10.2. Subject Assignment

Randomization will occur only after the subject has been determined to be eligible for study participation based on the inclusion and exclusion criteria. Subjects will be randomly assigned to one of the following five treatment groups in a 1:1:1:1:1 ratio: tolperisone 50 mg TID (150 mg/day), tolperisone 100 mg TID (300 mg/day), tolperisone 150 mg TID (450 mg/day), tolperisone 200 mg TID (600 mg/day), matching placebo TID. Prior to each eligible subject's participation, the next unique, sequentially available randomization number will be assigned to the subject using an interactive web response system.

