6.3.2 Method of Assigning Subjects to Treatment Groups

The study will be double-blinded. No treatment assignment information will be disclosed to any staff member (site, sponsor, or contract research organization) working on the trial, with the exception of the unblinded statistician and the pharmacovigilance representative in the event of emergency unblinding (only to be done when knowledge of treatment assignment is considered critical for patient care).

Subjects will be randomized to treatment group (150mg/day, 300 mg/day, 450 mg/day, 600mg/day or Placebo) in a 1:1:1:1:1 ratio and stratified by site. Upon confirmation that all study eligibility criteria have been met at Baseline (Day 0), unique randomization numbers will be assigned to subjects using an interactive web response system (IWRS) and the Investigator will

dispense a single bottle of tolperisone/placebo to the eligible patient. The assigned bottle number will be captured on the electronic case report form (eCRF).

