7.4.4 Primary Efficacy Endpoint Analysis Methods

The primary efficacy endpoint is NRS subject-rated pain “right now” due to acute back spasm on Day 14 for all subjects in the ITT population. This analysis will be performed using a linear test of trend across all tolperisone doses.

The null and alternate hypotheses to be tested are:

H₀: There is no significant trend in NRS rating of pain “right now” across dose groups

H₁: There is significant trend in NRS rating of pain “right now” across dose groups

The linear test of trend will be performed using a mixed effect model for repeated measures (MMRM) using an unstructured covariance matrix to model within-patient errors. However, if the computational algorithm fails to converge, other covariance structures will be evaluated (e.g., compound symmetry). The covariance structure converging to the best fit, as determined by Akaike’s information criterion, will be used. The Kenward and Roger method will be used to calculate the denominator degrees of freedom for the test of fixed effects. Based on this model, the hypothesis test described above will be tested using a two-sided test at the $\alpha=0.05$ level of significance.

The response variable will be the observed NRS rating of pain “right now”. The observed value on Day 14 is the primary time point of interest. The model will include factors for treatment group (5 levels: placebo, 150 mg/day, 300 mg/day, 450 mg/day and 600 mg/day) and visit (three levels: Day 1/Baseline, Day 4, and Day 14) as fixed effects, the treatment by visit interaction, and the baseline NRS rating as a covariate. The primary analysis will be based on all available data without imputation. Day 14 will reflect subjects that have completed the scheduled Day 14 (Visit 3). Subjects discontinuing the study may be analyzed as part of the sensitivity analysis using data imputation methods (LOCF and Multiple Imputation) to address missing data.

The observed NRS rating and change from baseline values will be presented using descriptive statistics for each treatment group by visit. The p-value for the overall test of trend on Day 14 will be presented. The pairwise least-square mean (LSM) estimates and least-square mean differences (LSMD) for each tolperisone dose level versus placebo will also be presented with 95% confidence intervals of the LSMD and associated p-values for the Day 14 visit observed values.

A plot of NRS subject rating of pain right now across study days will be presented.

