The number of subjects with relief and those censored will be summarized by treatment group for the ITT population. Estimates of the median times will be presented along with their associated 95% confidence intervals. Treatment group comparisons will be summarized with hazard ratios and their associated 95% CI from a Cox Proportional Hazards regression model with treatment as the main effect and p-values from a generalized Wilcoxon test.

The Kaplan Meier plots of time to pain relief by treatment group will be presented and display the subjects with relief and those censored at each study day.

A by subject listing of derived time to relief estimates will also be presented.

7.4.5.9 *Rescue Medication Use*

The use of study provisioned medication will be summarized using frequency counts and percentages for the number of tablets consumed by treatment group for the ITT population. Descriptive statistics will also be presented by treatment group. The number of days of medication use, average daily use (caplets/day of medication use) and total use will be tabulated using descriptive statistics. The frequency and percentage of subjects with rescue medication entry will be presented.

The Shapiro-Wilk test will be used to examine the assumption of normality for total rescue medication use across all dose groups. If this test is statistically significant (i.e., $p \leq 0.05$) then the assumption of normality is violated and the total rescue medication consumption will be analyzed using a Wilcoxon Rank Sum test.

However, if the assumption of normality holds (i.e., Shapiro-Wilk p-value > 0.05), then the total rescue medication consumption will be analyzed using an analysis of variance (ANOVA) model with randomized treatment as the main effect. The LSM and LSMD will be presented with associated 95% CI and p-values comparing each treatment group to placebo.

A data listing of rescue medication use will be presented and include the average number of tablets consumed and total number of tablets rescue medication consumed for each subject.

7.4.5.10 *Oswestry Disability Index*

ODI score (%) will be calculated as $(\text{total score} \times 2) / (\text{number of sections answered} / 10)$, rounded to the nearest integer, where the total score is the sum of the individual section scores.

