Observed ODI score and change from baseline will be summarized descriptively for each treatment group for the ITT population. Each dose group will be compared to placebo using an ANCOVA model with observed value as the response, main effects for treatment group and a covariate adjusted for the baseline ODI score. The LSM, LSMD, 95% CI and p-values will be presented at Day 14.

Individual section scores will be summarized separately for the ITT population by treatment group. The frequency and percentage of subjects in each response category at Baseline, Day 4 and Day 14 will be presented. The comparison of each group to placebo will be conducted using a Wilcoxon Rank Sum test for the Day 14 values and p-values presented.

7.4.5.11 *Visual Analogue Scale of Sleepiness*

The Day 4 VAS ratings of sleepiness will be summarized descriptively by treatment group for the ITT population. Each dose group will be compared to placebo using an ANOVA model with the observed values as the response and main effects for treatment group. The LSM, LSMD, 95% CI and p-values will be presented.

7.4.5.12 *Daily Activities*

Daily activity scores will be summarized categorically for Days 1 to 14 by treatment group for the ITT population. The frequency and percentage of subjects in each response category will be presented. The comparison of each group to placebo will be conducted using a Wilcoxon Rank Sum test for the Day 14 values and p-values presented.

7.4.6 *Statistical/Analytical Issues*

7.4.6.1 *Adjustments for Covariates*

The MMRM model to test for linear trend for the primary endpoint will include a covariate adjustment for the baseline value. Secondary endpoints utilizing an MMRM will be analyzed similarly when a baseline value is captured.

7.4.6.2 *Handling of Dropouts or Missing Data*

Primary and secondary endpoints including all NRS assessments (right now, past 12 hours, past 1 hour, at rest, on movement), Fingers to floor Distance, Clinician's Global Impression, and Oswestry Disability Index assessments will be analyzed using both observed data and data imputed using last observation carried forward (LOCF), if the dropout rate is $\geq 5\%$ (20/400 subjects). In the LOCF method, the most recent non-missing value for the endpoint is carried forward to replace a missing value at a post-baseline visit within a subject. Baseline values will not be carried forward.

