Methods for multiple imputation (MI) for missing data may be explored for endpoints if the dropout rate is $\geq 15\%$ (60/400 subjects).

7.4.6.3 *Interim Analyses and Data Monitoring*

There are no interim analyses planned, nor is there a plan to establish a data monitoring committee for this study.

7.4.6.4 *Multicenter Studies*

This is a multicenter study, with approximately 45 sites expected to participate. Efficacy data collected from all study sites will be pooled for data analysis. The effect of study site on the efficacy analysis results may be explored post-hoc, as needed.

7.4.6.5 *Multiple Comparisons/Multiplicity*

There will be no adjustments for multiple comparisons in the efficacy analysis for this study. All of the above analyses will be conducted using two-sided tests at the $\alpha = 0.05$ level of significance.

7.4.6.6 *Use of an “Efficacy Subset” of Subjects*

The primary efficacy analysis will be performed on the ITT population; the PP population will be utilized as a sensitivity analysis for the primary endpoint and secondary endpoints, including NRS (right now, past 12 hours, past 1 hour, at rest, on movement), Subject Rating of Medication Helpfulness, Fingers to Floor Distance, Clinician’s Global Impression assessments, and Oswestry Disability Index. The PP population will exclude subjects with major protocol violations.

7.4.6.7 *Active-Control Studies Intended to Show Equivalence*

This study does not include an active-control product and is not intended to demonstrate equivalence between any two drug products.

7.4.6.8 *Examination of Subgroups*

There are no planned analyses to assess efficacy results by subgroups.

7.4.7 *Plasma Concentrations*

Plasma concentration measurements will be summarized in a separate report and is outside the scope of this SAP.

7.4.8 *Pharmacokinetic Analysis*

Pharmacokinetic analysis will be summarized in a separate report and is outside the scope of this SAP.

7.5 **Safety Evaluation**

Safety analysis will be carried out for the Safety Population, which will include all subjects who receive at least one dose of study drug. Subjects who do not complete the study, for whatever reason, will have all available data up until the time of termination included in the analysis. For safety analysis presented by study visit, the baseline value will be defined as the last value reported prior to first study drug administration. All analyses will be presented by treatment group.

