7.6 Determination of Sample Size

The sample size for this study was determined from results of two previous studies. The first was a study in subjects with acute upper back, neck, or shoulder spasm and pain, which showed a difference of 0.4 in the average of Day 1 through Day 7 between the placebo and active groups, and standard deviations (SDs) between 1.76 and 1.93 (across placebo and active groups respectively; [Collaku, 2017](#)). A sample size of 400 subjects (80 per group) would provide at least 80% power to detect a difference of 0.9 between the placebo and treatment groups in the NRS scale, assuming a two-sample t-test at the 5% level of significance and a pooled SD of 2.0. This sample size assumes an effect size of 0.45 ($0.9/2.0 = 0.45$, using the formula $\text{Effect Size} = \text{Mean}/\text{SD}$), which is larger than that seen in the reference study but consistent with that seen in a second study.

A second previous study in subjects with acute musculoskeletal spasm associated with low back pain showed effect sizes ranging from 0.57 to 0.62 for lumbar cinesalgia, based on a treatment difference of 9.6 at Day 3, with SDs of 15.5 (treated group) and 16.7 (placebo group) (Chandanwale, 2011). This study demonstrated effect sizes ranging from 1.1 to 1.6, based on a difference of 24.2 at Day 14 with SDs of 15.1 (treated group) and 23.0 (placebo group). The effect size of the current study is expected to be similar to that in Chandanwale, though sample size estimates have been made more conservative to provide sufficient power to detect smaller differences. Though the primary comparison of interest in this study is Day 14, the study is sufficiently powered to detect a treatment difference at Day 4 based on effect sizes ranging from 0.35 to 0.45.

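### Randomisation is stratified by site, but no efficacy model includes site; if sites differ, a prespecified random site intercept would recover a little precision at almost no cost

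*SAP*

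**What the plan says.** SAP 6.3.2 assigns subjects to the five arms "in a 1:1:1:1:1 ratio and stratified by site". Protocol 10.2 gives the same ratio ("Subjects will be randomly assigned to one of the following five treatment groups in a 1:1:1:1:1 ratio") but does not mention stratification. It is silent rather than contradictory.

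The analysis sections do not carry site forward:

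- **Primary MMRM (SAP 7.4.4):** treatment and visit "as fixed effects, the treatment by visit interaction, and the baseline NRS rating as a covariate".
- **Covariates (SAP 7.4.6.1):** "The MMRM model to test for linear trend for the primary endpoint will include a covariate adjustment for the baseline value". No other covariate is named.
- **ODI ANCOVA (SAP 7.4.5.10):** "main effects for treatment group and a covariate adjusted for the baseline ODI score".
- **Time to relief (SAP 7.4.5.8):** "Cox Proportional Hazards regression model with treatment as the main effect".
- **Wilcoxon rank sum and generalized Wilcoxon tests (SAP 7.4.5):** no stratum is specified.
- **Multicenter section (SAP 7.4.6.4):** data are pooled over sites. "The effect of study site on the efficacy analysis results may be explored post-hoc, as needed".

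SAP 7.7.1, which lists changes in planned analyses, does not discuss site. The sample size in SAP 7.6 was also computed without it, "assuming a two-sample t-test at the 5% level of significance and a pooled SD of 2.0".

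**The concern.** A factor used to restrict the randomisation normally belongs in the analysis. Balancing arms within site means that differences between sites largely cancel out of the treatment contrasts, so the estimates vary less from trial to trial than they would under simple randomisation. A model without site does not register this. It counts between-site variation as residual noise, reports a standard error larger than the true one, and gives intervals that are too wide and p-values that are too large.

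What is at stake is efficiency and prespecification, not validity. The error is in the safe direction. However, the trial has a single trend test and four unadjusted dose comparisons from which to choose a Phase 3 dose, and it would give up some power that its design has already paid for. SAP section 4 says analyses are described in advance to avoid post-hoc decisions. A site adjustment left open until after the results are known is such a decision.

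**Working it through.** **Inputs from the documents.** 400 subjects, 80 per arm, five arms; about 45 sites (SAP 7.4.6.4); two-sided 5% level; pooled SD 2.0 and difference 0.9, so effect size 0.45 (SAP 7.6); trend power in Protocol Table 1. Average site size is 400/45 = 8.9 subjects, or 8.9/5 = 1.8 per arm per site.

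**Assumed, because the documents do not give them.** Site ICC 0 to 0.20; permuted blocks of 5 or 10 within site; trend scores (−2, −1, 0, 1, 2).

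**Step 1: reproduce the plan.**

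- High dose vs placebo: 0.9 / (2.0 × √(2/80)) = 2.846; power = Φ(2.846 − 1.960) = 81.2% (80.8% with noncentral t, 158 df). Table 1 gives 81%.
- Trend with effects 0, 0.1, 0.2, 0.3, 0.4 SD: contrast = −0.1 + 0.3 + 0.8 = 1.0; SE = √(10/80) = 0.3536; ratio θ = 2.828; power = Φ(2.828 − 1.960) = 80.7%. Table 1 gives 81%.
- With noncentral t, all 20 trend rows of Table 1 reproduce to within 0.6 points.

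**Step 2: place a share ICC of the variance between sites.** Hold total SD fixed, assume perfect balance within site, and let k = √(1 − ICC). The true SD of the contrast is k times the SE reported without site. Then:

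- SE ratio, without/with site = 1/k
- type I error without site = 2 × (1 − Φ(1.960/k))
- power without site = Φ((θ − 1.960)/k)
- power with site = Φ(θ/k − 1.960)

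For the trend, θ = 2.828:

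| ICC | SE ratio | Type I, no site | Power, no site | Power, with site | Gain (points) |
|---|---|---|---|---|---|
| 0 | 1.000 | 5.0% | 80.7% | 80.7% | 0 |
| 0.02 | 1.010 | 4.8% | 81.0% | 81.5% | 0.5 |
| 0.05 | 1.026 | 4.4% | 81.4% | 82.7% | 1.3 |
| 0.10 | 1.054 | 3.9% | 82.0% | 84.6% | 2.6 |
| 0.20 | 1.118 | 2.8% | 83.4% | 88.5% | 5.1 |

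High dose vs placebo at 0.45 gives nearly the same gains. For a flat response at 0.4 SD, which Table 1 puts at 62%, power at ICC 0.10 is 62.3% without site and 66.2% with it (noncentral t).

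**Step 3: express the gain in subjects.** Power without site on m × 400 subjects equals power with site on 400 when √m = 1 + 1.960 × (1 − k)/θ. At ICC 0.02, 0.05, 0.10 and 0.15, m = 1.014, 1.035, 1.072 and 1.111, which is about 6, 14, 29 and 44 extra subjects. These figures take no account of baseline adjustment.

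**Step 4: check by simulation** (45 sites, 400 subjects, single visit, REML random intercept, 3,000 to 4,000 runs per cell).

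- SE ratios at ICC 0.02 / 0.05 / 0.10 / 0.20 were 1.012 / 1.025 / 1.051 / 1.112 (equal sites, blocks of 5) and 1.009 / 1.022 / 1.045 / 1.104 (skewed sites, blocks of 10).
- At ICC 0.10 with no treatment effect and equal sites, the high-dose contrast had a true SD of 0.1485. The plan's model reported a mean SE of 0.1579; the random intercept reported 0.1503.
- Trend type I error at ICC 0.10 was about 4.0% without site and 4.8 to 5.3% with the intercept. The Monte Carlo error is about 0.4 points.
- At ICC 0 the intercept cost nothing (80.7% vs 80.9%, equal sites).

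**Step 5: allow for baseline NRS**, which the planned model does include. Assume a baseline-outcome correlation of 0.4, and a correlation of 0 / 0.5 / 0.9 between the baseline and outcome site effects. The gain is 1.4 / 0.7 / 0.6 points at ICC 0.05 and 3.1 / 1.6 / 0.8 points at ICC 0.10.

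**Step 6: allow for repeated visits.** Two-visit (Day 4, Day 14) unstructured REML models with baseline as covariate and complete data gave a Day 14 trend SE ratio of about 1.02 at ICC 0.05 and 1.03 to 1.06 at 0.10. Gains were about 1 point and 1 to 3 points, with no loss at ICC 0.

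**Step 7: compare the obvious alternative.** With about 45 unpooled fixed site effects, skewed sites and blocks of 10, the change in power was −2.1 points at ICC 0 (80.9% to 78.8%), −1.3 at 0.02, −0.6 at 0.05 and +0.8 at 0.10.

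**The case against.** The case for leaving the plan alone is reasonable. The planned test is valid, its power is as stated, and SAP 7.4.6.4 states openly that sites will be pooled. Stratification already makes the estimate itself more precise, and the intercept hardly changes its true SD; only the reported uncertainty improves. The size of the gain depends on an ICC that the documents do not give, and at ICC 0 to 0.02 it is negligible. Figures that ignore baseline NRS overstate it when baseline carries the same site differences. A later exploratory site analysis could not displace the prespecified primary result.

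All of this stands as a limit on weight. The results at ICC 0.15 and 0.20 show the direction of the effect and are not forecasts. The baseline-adjusted gains in step 5 are closer to the planned model.

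One technical reservation also remains. SAP 7.4.4 lists Day 1/Baseline as a level of visit while using baseline as a covariate. That exact form was not simulated, so the absence of power loss is shown for closely related models and not for the SAP's literal one.

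The objection does not supply a reason for omitting the design factor, and the SAP does not give one either.

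**Conclusion.** The point holds, as something to consider rather than an error. Site is used to randomise and appears in no planned efficacy analysis. If sites differ, the planned standard errors are conservative: by about 2% at ICC 0.05 and about 3 to 6% at ICC 0.10 in the repeated-measures checks. The power forgone is roughly 1 point and 1 to 3 points respectively, and nil at ICC 0. Sample size, stated power and type I control are not in question.

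The result assumes complete Day 14 data, near-balance within sites, and the ICCs and correlations stated above. If allocation were not in fact stratified, type I error without site would be about nominal, and the intercept would still gain 0.3, 0.6, 1.8 and 5.1 points at ICC 0.02, 0.05, 0.10 and 0.20.

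**What to change.** Before unblinding, amend SAP 7.4.4 and 7.4.6.4 to include site as a random intercept in the primary MMRM and the other continuous models (the secondary MMRMs, ANCOVA and ANOVA). State a fallback for non-convergence, for example a site factor after pooling small sites by a rule fixed in advance. Do not enter about 45 unpooled fixed site effects. Stratifying the Cox model and rank tests by pooled site is optional; no gain was calculated for them.

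If the sponsor prefers to keep site out of the primary model, the SAP should give the reason and prespecify the random-site model as a sensitivity analysis. Protocol 10.2 should also mention stratification by site, to match SAP 6.3.2.

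The cost is wording, one random term and a fallback rule, with no extra subjects or procedures. The drawback is a slightly more complex model that may need the fallback.

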6.4 Efficacy and Safety Variables

6.4.1 Efficacy Variable

6.4.1.1 Primary Efficacy Variable

The primary efficacy endpoint is subject-rated pain “right now” due to acute back spasm using a Numerical Rating Scale (NRS; a scale of 0-10 where 0 = no pain and 10 = worst possible pain) on Day 14.

6.4.1.2 Secondary Efficacy Variables

Secondary efficacy endpoints include assessments administered on a study-provisioned tablet at the clinical site on Day 1 (baseline), Day 4, and Day 14 or captured by the subject with smartphone/trial application daily at home from Day 1 to Day 14 (See Table 2)

- Subject-rated pain due to acute back spasm “right now” using NRS on Day 4
- Subject-rated average pain due to acute back spasm over past 12 hours using NRS on Days 1 to 14, measured in morning and evening.
- Subject-rated average pain due to acute back spasm over past 1 hour using NRS on Days 1 to 14, measured in morning and evening
- Subject-rated average pain at rest due to acute back spasm using NRS on Days 1 to 14, measured in evening
- Subject-rated average pain on movement due to acute back spasm using NRS on Days 1 to 14, measured in evening
- Subject rating of medication helpfulness (SRMH) using a scale of 1-5 on Days 4 and 14, where 1=poor, 2=fair, 3=good, 4=very good, and 5=excellent.
- Time to relief of pain due to acute back spasm (days) from baseline using subject-rated NRS of pain over past 12 hours. The first NRS score of 2 or lower will be used to define relief.
- Clinician’s Global Impression of Severity (CGI-S) using 1–5 scale at baseline (Day 1), where 1=no pain, 2=mild pain, 3=moderate pain, 4=severe pain, and 5=worst possible pain
- Clinician’s Global Impression of Change (CGI-C) using a scale of 1-7 on Days 4 and 14, where 1=Very Much Worse, 2=Much Worse, 3=Minimally Worse, 4=No Change, 5=Minimally Improved, 6=Much Improved, and 7=Very Much Improved

- Patient's Global Impression of Severity (PGI-S) using a scale of 1–5 scale at baseline (Day 1), where 1=no pain, 2=mild pain, 3=moderate pain, 4=severe pain, and 5=worst possible pain
- Patient's Global Impression of Change (PGI-C) based on subject's global assessment using a scale of 1-7 on Days 4 and 14, where 1=Very Much Worse, 2=Much Worse, 3=Minimally Worse, 4=No Change, 5=Minimally Improved, 6=Much Improved, and 7=Very Much Improved).
- Fingers to floor distance (FFD) measured at Baseline (Day 1), Day 4, and Day 14

FFD is an index of mobility of the spinal cord and is measured as distance in cm when standing with the spinal cord flexed with complete extension of knee joint, on Days 4 and 14 compared to baseline (Day 1) (assessments should be conducted at the same time of day for all three time points).

- Oswestry Pain and Disability (ODI) assessment at baseline (Day 1), Day 4, and Day 14

The ODI questionnaire contains 10 questions with one answer each for pain intensity, personal care, lifting, walking, sitting, standing, sleeping, sex life [if applicable], social life, and traveling). Scores are assigned for each section from 0 to 5 (5 being the worst case).

ODI scores are derived based on the methods described in [Mehra et.al. \(2008\)](#). The method is equivalent to an ODI score calculated as $(\text{total score} \times 2) / (\text{number of sections answered} / 10)$, rounded to the nearest integer. The total score is the sum of the individual section scores.

- Use of study-provided rescue medication [acetaminophen tablets (500 mg)] measured daily and assessed as number of rescue tablets administered by the subject and recorded via smartphone/use of trial application.
- Quality of sleep as rated by subjects daily from Day 1 to Day 14. The rating scale is 1-5, where 1 = not at all to 5 = slept all night. Assessments are collected via smartphone/use of trial application.
- Visual Analogue Scale (VAS) for subject-reported sleepiness as measured in the clinic on at Day 4 via tablet ePRO. Scale is from 0 to 10, where 0 = alert, wide awake to 10 = very sleepy, difficulty remaining awake.

6.4.2 *Description of Safety Variables*

Safety variables include:

- Adverse events and serious adverse events

- Clinical evaluations including vital signs (blood pressure, heart rate, respiratory rate, body temperature), orthostatic effects on blood pressure, physical examinations, and 12-lead electrocardiogram (ECG)
- Laboratory tests including blood chemistry, hematology, and urinalysis

6.4.2.1 *Adverse Events*

An AE is defined as any untoward medical occurrence in a subject administered a medicinal product and which does not necessarily have to have a causal relationship with this treatment. An AE can therefore be any unfavorable and unintended sign (for example, an abnormal laboratory finding), symptom, or disease temporally associated with the use of a medicinal product, whether or not considered related to this medicinal product. AEs occurring after the initiation of the study drug treatment are referred to as treatment-emergent adverse events (TEAEs).

See Section 15.1 of the study Protocol for further details regarding the definition of AEs.

6.4.2.2 *Serious Adverse Events*

An SAE or reaction is any untoward medical occurrence that at any dose:

- Results in death,
- Is life-threatening,
- Requires inpatient hospitalization or prolongation of existing hospitalization,
- Results in persistent or significant disability or incapacity (defined as a substantial disruption of a person's ability to conduct normal life functions),
- Is a congenital anomaly or birth defect,
- Is an important medical event (including development of drug dependence or drug abuse) that may jeopardize the subject or may require intervention to prevent one of the other outcomes listed above (according to medical judgment of the Principal Investigator).

See Section 15.3 of the study Protocol for further details regarding SAEs and reporting.

6.4.2.3 *Laboratory Parameters*

A central laboratory will perform all laboratory testing. [Table 3](#) lists all planned clinical laboratory tests to be performed.

Table 3 Clinical Laboratory Assessments

Category	Test Name
Hematology	Hemoglobin Hematocrit Platelets Prothrombin Time (PT) ^a Red blood cells White blood cells with differential (absolute)
Chemistry	Alanine aminotransferase (ALT) Aspartate aminotransferase (AST) Alkaline phosphatase Blood urea nitrogen (BUN) Creatinine Gamma glutamyltransferase (GGT) Glucose Potassium Sodium Total and direct bilirubin Thyroid stimulating hormone (TSH) ^a
Urinalysis	Bilirubin Occult blood Glucose Ketones Leukocytes Nitrite pH Protein Specific gravity Urobilinogen
Other	Urine drug and alcohol breathalyzer ^{b,c} Urine pregnancy ^d

Note: The complete panel of safety labs (other than where footnoted) will be completed on Day 1 (Screening/Baseline visit) and Day 14.
 
a Screening only.
 
b Day 1 (Screening/Baseline), Day 4, and Day 14 (End of Treatment).
 
c Includes testing for amphetamines, methamphetamines, barbiturates, benzodiazepines, cannabinoids, cocaine, opiates – ethanol will be determined by breathalyzer.
 
d Urine pregnancy test at Days 1, 14, and 28 for females of childbearing potential.
	

6.4.2.4 *Other Safety Variables*

